## **2. Definitions and classification of covariates**

The covariates used in the incremental models include measures of stroke severity, demographic factors, and traditional cerebrovascular risk factors.

- Measures of stroke severity
  - Discharge location, classified as discharged home vs. not home (skilled nursing, rehabilitation center, etc.).

- Discharge mRS, categorized as 0, 1, 2, 3 or 4 or more (noting relatively few patients with discharge mRS of 5).
- Discharge NIH Stroke Scale (NIHSS), categorized into approximate quartiles of 0, 1, 2-4 or 5+
- Stroke subtype (hemorrhage vs. infarction)
- Demographic factors
  - Age, considered as a continuous factor
  - Male sex
  - Race/Ethnicity, categorized as non-Hispanic white (NHW) versus not NHW (including both other races and Hispanic participants)
  - A summary neighborhood index of socio-economic status (nSES) based on previously published methods, including six variables representing wealth/income, education and occupation: (1) log of median household income, (2) log of median value of owner-occupied housing units, (3) proportion of households receiving interest, dividend, or net rental income, (4) proportion of adults aged  $\geq 25$  years with a high school diploma, (5) proportion of adults aged  $\geq 25$  years with college degree, and (6) proportion of people employed in executive, managerial or professional occupations.
- Baseline cerebrovascular risk factors
  - Cigarette smoking, categorized as current vs. non-current (past or never)
  - Hypertension as a dichotomous variable
  - Dyslipidemia as a dichotomous variable
  - Diabetes as a dichotomous variable
  - Atrial fibrillation or irregular heartbeat as a dichotomous variable
  - Sedentary activity (defined as a score of 0-No Physical Activity or 1-Sedentary or sitting most of the time)

Because the mixed models will include baseline assessment of the outcome variable (i.e., outcomes include measures at times 0, 3, 6, and 12 months), covariates directly related to the outcome being assessed will be excluded from the model. That is, variables will not be used as both an outcome and as a predictor in the same model. For example, discharge mRS will not be included in the models predicting treatment differences in mRS, and baseline hypertension will not be included in models assessing treatment differences in SBP. Rather, changes from baseline to the 3, 6 and 12-month visits will be assessed using contrast statements.

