### **3. Primary Outcome Analyses**

#### **3.1. Analysis of intermediate factors**

Because the ISPU intervention was targeted to specific groups determined by baseline assessments, the primary analysis of the six intermediate factors will be restricted to the estimation of treatment differences among patients who were not in control at discharge, specifically assessing the percentage of patients with:

- 1) SBP below 130 mmHg at 3, 6, and 12-months among those with SBP of 130 mmHg or above at discharge
- 2) LDL below 70 mg/dL at 3, 6, and 12-months among those with LDL of 70 mg/dL or above at discharge

- 3) HbA1c below 7% at 3, 6, and 12 months among those with HbA1c of 7% or above at discharge
- 4) Smoking cessation at 3, 6, and 12-months among those smoking at dischargement,
- 5) Adhering to a Mediterranean or DASH diet among those not adhering at baseline
- 6) Having regular exercise levels of moderate or above among those with lower levels at baseline.

The primary hypothesis will focus on compliance/adherence at the 12-month visit, but mixed models will be used with assessments at the 3 time points (3, 6, and 12 months) and treatment differences reported at all three follow-up times.

Analyses will generally take the approach of using a mixed model approach with: 1) repeated measures at 3, 6 and 12 months, and 2) a random effect for patient and site (if models do not converge, site will be considered as affixed effect). As all of the intermediate factors will be dichotomized for the follow-up assessments, outcomes will be assessed using PROC GLIMMIX. Treatment differences will be assessed in a series of incremental models: 1) crude, 2) adjusted for stroke severity, 3) further adjustment for demographics, and 4) adjustment for cerebrovascular risk factors (see section 2 for factors in each group). The temporal pattern of treatment differences at 3, 6 and 12-months will be described by the treatment-specific proportion adherent/compliant with 95% confidence intervals. The primary assessment of treatment efficacy will be the p-value and confidence intervals for the treatment difference in the proportion at the 12th months; however, p-values and confidence intervals for months 3 and 6 will also be reported.

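### The rule excluding outcome-related covariates assumes a month-0 outcome that the restricted intermediate-factor models lack, so discharge level of SBP, LDL or HbA1c above target goes unadjusted

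*SAP*

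**What the plan says.** SAP section 2 lists the covariates for the incremental models. For the three laboratory or blood-pressure factors the list holds yes/no entries only: "Hypertension as a dichotomous variable", "Dyslipidemia as a dichotomous variable" and "Diabetes as a dichotomous variable". Discharge SBP in mmHg, LDL in mg/dL and HbA1c in % are not on it.

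The same section then sets an exclusion rule: "covariates directly related to the outcome being assessed will be excluded from the model". The reason given is "Because the mixed models will include baseline assessment of the outcome variable (i.e., outcomes include measures at times 0, 3, 6, and 12 months"), with change from baseline to be taken by contrasts. One example is that "baseline hypertension will not be included in models assessing treatment differences in SBP".

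SAP 3.1 defines the primary analysis of the six intermediate factors among patients not in control at discharge (SBP 130 mmHg or above, LDL 70 mg/dL or above, HbA1c 7% or above, and so on). The model has "repeated measures at 3, 6 and 12 months" and random effects for patient and site. The primary assessment is the treatment difference in the proportion controlled at month 12. A supplemental whole-population analysis uses months 0, 3, 6 and 12.

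SAP section 1 describes the models for the two primary outcomes and the six factors as including the baseline assessment. It justifies the incremental adjustment by the possibility that cluster randomization leaves key factors unbalanced.

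**The concern.** The rule makes sense where month 0 is one of the modelled outcomes, because the baseline information then stays in the model. In the restricted models it does not: month 0 is absent, and it would carry no information if added in dichotomised form, since every patient in the subset is out of control by selection. The discharge level is therefore neither outcome nor covariate, and the rule as worded would also bar an analyst from adding it.

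A patient discharged just above 130 mmHg and one discharged far above it differ in no SBP-related term at any adjustment level. Baseline hypertension is removed from the SBP model by name. Under the general rule, dyslipidemia would likewise leave the LDL model and diabetes the HbA1c model, although the SAP does not say so explicitly.

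The SAP treats these six factors as integral to the assessment of the primary outcomes, and adjusts precisely because 21 sites may not balance. Distance above target is a plausible candidate for such imbalance, and the planned series of models does not reach it.

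**Working it through.** **Which model carries the discharge value.**

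| Model | Time points | Role of the discharge value |
|---|---|---|
| mRS, SIS (SAP 3.2, 3.3) | 0, 3, 6, 12 | Outcome at month 0 |
| Six factors, whole population (SAP 3.1, supplemental) | 0, 3, 6, 12 | Outcome at month 0, dichotomised |
| Six factors, not in control at discharge (SAP 3.1, primary) | 3, 6, 12 | Defines entry at the cut-off; otherwise absent |

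The reason given in section 2 fits the first two rows and not the third. Section 1 describes the six factors as if they all belonged to the first two rows.

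**Size, for SBP.** There is no figure in the plan to reproduce: the documents give no SD, correlation or control rate for these factors. All inputs below are assumptions except the 21 sites (SAP section 1) and the 130 mmHg cut-off (SAP 3.1).

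- Discharge SBP X ~ N(138, 17); 12-month SBP Y ~ N(133, 17); correlation r = 0.3 to 0.5; no treatment effect.
- Observed site means of discharge SBP have SD 3 to 5 mmHg; sites split 10 and 11.

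*Step 1: control given discharge level.* P(Y < 130 | X = x) = Φ{[130 − 133 − r(x − 138)] / [17√(1 − r²)]}. Averaged over discharge bands:

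| r | Discharge 130–139 | Discharge 150 or more |
|---|---|---|
| 0.3 | 45% | 28% |
| 0.5 | 46% | 18% |

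*Step 2: chance difference between arms, all patients.* 95% limit = 1.96 × SD × √(1/10 + 1/11) = 1.96 × SD × 0.437. SD 3 gives 2.6 mmHg; SD 5 gives 4.3 mmHg.

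*Step 3: the same difference after restriction to X ≥ 130.* The truncated mean is 146.9 when the overall mean is 138, 148.2 when it is 140.6 and 149.1 when it is 142.3. The differences are 1.3 and 2.2 mmHg, about half of those in step 2.

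*Step 4: effect on percent controlled.* Averaging step 1 over the truncated distributions:

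| r | No shift | Shift 2.6 | Shift 4.3 |
|---|---|---|---|
| 0.3 | 36.7% | 35.8% (0.9 points) | 35.2% (1.4 points) |
| 0.5 | 32.1% | 30.7% (1.3 points) | 29.8% (2.3 points) |

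*Sensitivity to the assumptions.* With discharge SBP N(140, 20), 12-month mean 132 and SD 20, overall shifts of 3 to 8 mmHg (1.5 to 4.3 mmHg after restriction) give 0.6–1.7 points at r = 0.2, 1.2–3.2 at r = 0.4 and 1.7–4.6 at r = 0.6. In this set-up, adding the continuous discharge value removes the difference. No corresponding calculation was made for LDL or HbA1c.

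**The case against.** Four points weigh on the other side.

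*Sites are randomised and the model has a random site effect.* Chance differences between sites, including in discharge level, add to the site variance and so to the confidence interval. A reader might infer that the analysis is biased or its test invalid. The documents do not support that: over repeated randomisations the chance imbalance is sampling error. What stands is that, in the one trial actually run, an imbalance in discharge level would not be corrected, and the precision available from the covariate is given up.

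*The discharge value is not wholly ignored.* Restriction at the cut-off conditions on it, and the supplemental analysis carries it as a dichotomised month-0 outcome. To say it is never adjusted for would be too strong. Neither step, however, addresses level within the uncontrolled group.

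*Nothing was removed that had been listed.* A reader of section 2 might conclude that the SAP drops measured discharge SBP, LDL and HbA1c. These were never on the covariate list. They are omitted, and the related yes/no risk factor is what the rule takes out.

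*The prognostic weight is assumed.* It is tempting to call discharge level the strongest predictor of 12-month control. Nothing in the documents shows this; the illustration rests on assumed correlations.

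**Conclusion.** The point holds in limited form. The reason given in SAP section 2 does not apply to the restricted models in SAP 3.1, and discharge level above target is unadjusted at all four levels for SBP, LDL and HbA1c. This follows from the text and needs no assumption. The conflict between SAP sections 1 and 3.1 over whether baseline is modelled is also on the page.

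The size is modest and rests entirely on assumed inputs: about 0.9 to 2.3 percentage points in SBP control at the 95% limit of chance imbalance. A reader who applied the 2.6 to 4.3 mmHg range directly to the restricted group would get roughly double that, but the range describes all patients and shrinks on truncation at 130 mmHg.

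A reader might also extend the concern to mRS and SIS. That does not follow, since both are modelled with month 0 as an outcome. The change is worth making for precision and conditional balance; the planned inference is not invalid without it.

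**What to change.** 1. In SAP section 2, limit the exclusion rule to models that include month 0 as an outcome.
2. In SAP 3.1, for the restricted models of SBP, LDL and HbA1c at months 3, 6 and 12, add the patient's own discharge value as a continuous covariate in the adjusted models. Keep the crude model as an unadjusted display.
3. Reconcile the SAP section 1 statement that the six factors are modelled with baseline included with the three-time-point model in section 3.1.

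The cost is a few lines of SAP text and one term per model. No new data are needed: the discharge value is observed for every patient in the restricted set, because it defines that set.

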### **3. Primary Outcome Analyses**

#### **3.1. Analysis of intermediate factors**

Because the ISPU intervention was targeted to specific groups determined by baseline assessments, the primary analysis of the six intermediate factors will be restricted to the estimation of treatment differences among patients who were not in control at discharge, specifically assessing the percentage of patients with:

- 1) SBP below 130 mmHg at 3, 6, and 12-months among those with SBP of 130 mmHg or above at discharge
- 2) LDL below 70 mg/dL at 3, 6, and 12-months among those with LDL of 70 mg/dL or above at discharge

- 3) HbA1c below 7% at 3, 6, and 12 months among those with HbA1c of 7% or above at discharge
- 4) Smoking cessation at 3, 6, and 12-months among those smoking at dischargement,
- 5) Adhering to a Mediterranean or DASH diet among those not adhering at baseline
- 6) Having regular exercise levels of moderate or above among those with lower levels at baseline.

The primary hypothesis will focus on compliance/adherence at the 12-month visit, but mixed models will be used with assessments at the 3 time points (3, 6, and 12 months) and treatment differences reported at all three follow-up times.

Analyses will generally take the approach of using a mixed model approach with: 1) repeated measures at 3, 6 and 12 months, and 2) a random effect for patient and site (if models do not converge, site will be considered as affixed effect). As all of the intermediate factors will be dichotomized for the follow-up assessments, outcomes will be assessed using PROC GLIMMIX. Treatment differences will be assessed in a series of incremental models: 1) crude, 2) adjusted for stroke severity, 3) further adjustment for demographics, and 4) adjustment for cerebrovascular risk factors (see section 2 for factors in each group). The temporal pattern of treatment differences at 3, 6 and 12-months will be described by the treatment-specific proportion adherent/compliant with 95% confidence intervals. The primary assessment of treatment efficacy will be the p-value and confidence intervals for the treatment difference in the proportion at the 12th months; however, p-values and confidence intervals for months 3 and 6 will also be reported.

In addition to this primary analysis of the intermediate factors that is restricted to those not compliant/adherent at discharge, a supplemental analysis will assess the proportion compliant at 3, 6, and 12 months regardless of compliance at month 0 (i.e., proportion compliant/adherent in the entire population). This analysis will consider a mixed modeling approach with outcomes at 4 time points (0, 3, 6, and 12 months). The focus of this analysis will be on the change in the proportion compliant between month 0 and 12 months (but also reporting the change in the proportion to 3 and 6 months). In addition to assessing treatment differences in the change in the proportion, the treatment differences in the proportions at the 4 time points will be assessed.

For all six factors, analyses assessing the potential for bias from missingness will be performed using inverse probability weighting (for both the analysis restricted to those not compliant/adherent and for the entire population analysis). This will be conducted by first developing a logistic regression model estimated in all subjects predicting the probability of observing the 12-month observation. Predictors in the model will be site (with cluster randomization, implicitly including treatment effect), age, NHW race/ethnicity, sex, NIHSS and nSES. The inverse of this probability will be standardized by dividing by the sum of the inverses, standardizing the inverse probabilities to have the same sum as the sample size; hence, not inflating or deflating statistical power. The analysis for the factor will then be repeated using the inverse probability weights. Should the interpretation of results differ between the weighted and unweighted analyses, the primary interpretation will be based on the weighted analysis, and the weighted analysis will be the basis for figures and estimates in the manuscript will focus on the weighted results.

Effect modification will be assessed by age, sex, race/ethnicity, stroke sub-type, stroke severity (discharge NIHSS dichotomized at 0 to 1 versus 2+), and nSES.

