Analysis of the primary analysis will focus on intervention differences in mean SIS and smRS scores at 12 months. In addition, the mixed models will be used to assess the SIS and smRS outcomes at 12 months, allowing the hierarchical nature of the data to be reflected (patients within Sites), and providing an accounting for data that are not missing completely at random. Analyses of the secondary outcomes of time either rehospitalization or subsequent stroke will be assessed using proportional hazards analysis. In order to incorporate the hierarchical nature of these data, this analysis will be implemented using packages such as the SURVIVAL procedure from the SUDAAN package (Research Triangle Institute, Research Triangle Park, NC).

Analysis of the QOL secondary outcome will follow the analysis approach as the primary analysis and will have similar power (i.e., ability to detect intervention differences of magnitude of a half-standard-deviation). The study will also focus on identifying specific subgroups who are particularly responsive or resilient to intervention differences.

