## **1. Introduction**

C3FIT is a cluster -randomized clinical trial randomizing 24 sites (21 of which provided data and will be included) to assess the effectiveness, defined at 12-months post-stroke discharge, of post-stroke care delivered using the Joint Commission (JC)-certified Comprehensive or Primary Care (CSC/PSC) model compared to an integrated, coordinated, technology-enabled Integrated Stroke Practice Unit (ISPU) model (that includes CSC/PSC care). The trial has two primary outcomes, the modified Rankin score (mRS) and the Stroke Impact Scale (SIS), both assessed at baseline (for SIS, only in approximately 50% of the participants), and at 3, 6 and 12 months. Any beneficial treatment effect of the ISPU approach on the mRS and SIS is presumed to be through a beneficial effect on “intermediate” factors, specifically better control of: 1) systolic blood pressure (SBP) to levels below 130 mmHg, 2) LDL levels to levels below 70 mg/dL, 3) HbA1c to levels below 7%, 4) smoking cessation, 5) adherence to AHA diet guidelines by following a Mediterranean-type or DASH diet, and 6) adherence to AHA exercise guidelines by a usual exercise level of moderate or above. Each of these intermediate factors will be assessed among those failing to be in control at hospital discharge (i.e., for SBP, among those with discharge SBP $\geq$ 130 mmHg; for LDL, among those with discharge LDL levels above 70 mg/dL, etc.). Because of this presumed pathway for potential effects, the assessment of treatment effects on these six intermediate factors is considered an integral part of the assessment of primary outcomes. Because the cluster-randomization may fail to balance the treatment groups on key factors potentially affecting outcome, treatment differences will be assessed after a series of incremental models, first in a crude model with no adjustment, then with adjustment for measures of stroke severity, then with further adjustment for demographic factors, and then with further adjustment for major cardiovascular risk factors. Treatment differences for both the two primary outcome variables and the six intermediate factors will be assessed using a mixed model approach including the assessments at baseline, 3 months, 6 months and 12 months.

Beyond the intermediate factors above, the study also has secondary outcomes including mortality, recurrent stroke, rehospitalization, time at home, depression, caregiver strain, and perceived support.

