### **3.2. Modified Rankin Score (mRS)**

The mRS is a 7-point scale, ranging from 0 (normal) to 6 (dead), where at baseline the scores were from 0 to 5 (discharged dead were excluded from the study). During follow-up, patients were scored a 6 at the 3, 6 and 12-month follow-up if the patient died before the respective follow-up (even if the patient missed intervening visits). The mRS will be dichotomized as “good outcomes” of 0 to 2 points, and “poor outcomes” of 3 to 6 points. Analysis will use a mixed model approach (implemented through GLIMMIX) with the treatment-specific proportion of “good outcomes” modeled at months 0, 3, 6, and 12 (reported with the p-value for treatment differences at each time point). The primary outcome will be treatment differences in the change in the proportion with good outcomes between months 0 and 12, but differences to months 3 and 6 will also be estimated. These differences will be estimated with the same 4-level incremental adjustments, and with both unadjusted and inverse-probability weighted adjustment. Effect modification will be assessed by age, sex, race/ethnicity, stroke sub-type, stroke severity (discharge NIHSS dichotomized at 0 to 1 versus 2+), and nSES. With the discharge mRS as an outcome, the analysis will not be adjusted for baseline mRS.

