### **3.3. Stroke Impact Scale (SIS)**

The SIS is a continuous outcome variable with a range from 0 to 100 which will be analyzed identically to continuous intervening factors measured at 4 timepoints (including the analysis with inverse probability weighting). We do note that: 1) after approximately half the patients were recruited, a decision was made to not collect SIS at baseline; however, it is quite reasonable to assume that this decision will give rise to data missing at random and the missingness will be addressed by the mixed models, and 2) the baseline SIS collected were the “long form” of the questionnaire (96 items); however, the 16 items in the short form used at 3, 6 and 12 months are a subset of the long form, and these items will be extracted and scored identically with the follow-up assessments. The analysis of SIS will employ analysis for a continuous factor, but will follow the modeling approach described above for mRS, specifically reporting treatment differences in mean SIS rather than treatment differences in the proportion with good mRS outcome (primary outcome as treatment difference in the change in mean SIS between baseline and 12 months, 4-level incremental models, with/without inverse probability weighting, assessment of effect modifiers, etc.).

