## **4. Secondary Outcomes**

### **4.1. Time-to-event secondary outcomes (mortality, recurrent stroke, and rehospitalization)**

The number of days between discharge and death, recurrent stroke or rehospitalization will be calculated, and treatment differences in the times will be assessed using hierarchical proportional hazards models (i.e., using a RANDOM statement for site if conversion, or fixed effect with no conversion). The same incremental modeling approach (crude, adjusted for stroke severity, further adjusted for demographics, and finally adjusted for risk factors) will be employed. It is possible that the number of events may be relatively small (particularly for death and recurrent

stroke), introducing concerns for the use of too many covariates relative to the number of predictors. Should this be the case, a “restricted” number of covariates will be considered, specifically using NIHSS as the single index of severity, using age and race/ethnicity as the indexes of demographics, and hypertension as the single index of risk factors. These will be added in this order up to the point where there are at least 10 events for each factor introduced (i.e., perhaps, not even all these predictors can be considered).

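### The fixed-site fallback in SAP 3.1 and 4.1 makes visit-level treatment differences and hazard ratios non-estimable, and the only site term named gives the mRS and SIS change contrasts no between-site variance

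*SAP*

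**What the plan says.** Randomisation is by facility (Protocol 4.B). The SAP Introduction describes "randomizing 24 sites (21 of which provided data and will be included".

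- **Site term.** SAP 3.1 names "a random effect for patient and site (if models do not converge, site will be considered as affixed effect". SAP 4.1 has the same rule for death, recurrent stroke and rehospitalisation: "using a RANDOM statement for site if conversion, or fixed effect with no conversion".
- **Intermediate factors (3.1).** Efficacy is judged on "the p-value and confidence intervals for the treatment difference in the proportion at the" twelfth month. This is a difference in level, not in change.
- **mRS (3.2).** "The primary outcome will be treatment differences in the change in the proportion with good outcomes between months 0 and 12". Treatment p-values are also to be reported at each time point.
- **SIS (3.3).** The contrast is described as "primary outcome as treatment difference in the change in mean SIS between baseline and 12 months", and the analysis "will follow the modeling approach described above for mRS".
- **Not stated.** Sections 3.2 and 3.3 do not restate the random effects. The SAP names no site-by-time effect, no robust variance and no site-based degrees of freedom. Sections 4.3 to 4.5 contain no fallback of their own but refer back to the approaches used earlier in the SAP.

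**The concern.** Because each site is wholly in one arm, the arm indicator is a sum of site indicators. A model with site fixed has nothing left with which to estimate a treatment effect on level. The SAP comes close to saying this itself: its weighting model for missing data includes site and notes that site already carries treatment.

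The contrasts affected include the 12-month contrast for the six intermediate factors, which the SAP Introduction treats as integral to the primary assessment. The fallback also sits badly in 4.1. That section wants at least 10 events per factor introduced, yet fixed site adds 20 parameters for 21 sites.

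The second issue does not depend on the fallback. In a site-randomised trial the treatment effect must be judged against variation between sites. For mRS and SIS the primary contrast is a change, and the only site term named would normally be read as an intercept, which subtracts out of a change. If sites differ in 12-month recovery, that variation is missing from the standard error and the interval is too narrow.

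**Working it through.** **1. Inputs.** From the documents: 21 sites analysed (SAP Introduction); 1,262 patients (Protocol Summary), so 1,262/21 = 60.1, taken as 60 per site; SIS SD 8; ICC 0.05 as the working value, 0.10 as large, and 0.01 as the value the investigators think likely (Protocol 9.A). Assumed, because not stated: 11 versus 10 sites, equal site sizes, two-sided alpha 0.05, within-patient correlation ρ = 0.5, and the share s of site variance that is site-by-time.

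**2. The protocol's own figure.** With 9 sites per arm and 100 patients per site,

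SE = √[2 × 8² × (1 + 99 × ICC)/(9 × 100)],

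which is 0.920 at ICC 0.05 and 1.245 at ICC 0.10. A noncentral t with 18 − 2 = 16 df gives detectable differences of 2.745 and 3.178 (80% and 90% power) at ICC 0.05, and 3.716 and 4.302 at ICC 0.10. The protocol states 2.7, 3.2, 3.7 and 4.3. A normal reference gives only 2.58, 2.98, 3.49 and 4.04. So the trial was powered for a difference in 12-month level, with between-site variance in the SE and site-based df.

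**3. Fixed site.**
- One record per patient: intercept plus 20 site indicators has rank 21. Adding arm leaves it at 21.
- Visits 3, 6 and 12: 21 site columns plus 6 arm-by-visit columns make 27, with rank 25. With month 0 added: 29 columns, rank 27.
- Adding a constant to every ISPU site effect and subtracting it from every ISPU visit mean leaves the fit unchanged. The 12-month difference is therefore not estimable. The difference in change from month 0 to 12 is, because the constant cancels.
- If software drops columns and still prints an arm coefficient, it reflects only the reference sites. In one simulated data set it was −2.32, 0.35 or −2.82 for three choices of reference sites.

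**4. Random site intercept.** In the linear model, with patient-level variance held at 60.8:

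| Site variance | SE, change 0 to 12 | SE, 12-month level |
|---|---|---|
| 0.01 | 0.440 | 0.44 |
| 3.2 (ICC 0.05) | 0.440 | 0.90 |
| 19.2 | 0.440 | 1.96 |

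The change SE ignores the site variance. With half the baselines missing, as for SIS, it is 0.561 in all three rows.

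**5. Type I error of the change contrast.** Let V = 64 × ICC be the site variance. Per-patient change variance is C = 2(64 − V)(1 − ρ); site change variance is S = 2sV.

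- True variance = (C/60 + S)(1/11 + 1/10).
- Model variance = [(C + 0.906 S)/60](1/11 + 1/10). The pooled within-arm patient variance picks up (1,260 − 120)/1,258 = 0.906 of S.
- Type I error = 2[1 − Φ(1.96 × SE model/SE true)].

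Example, ICC 0.05 and s = 20%: V = 3.2, C = 60.8, S = 1.28. True SE = √[(1.0133 + 1.28) × 0.1909] = 0.662; model SE = 0.444; 1.96 × 0.444/0.662 = 1.315, giving 18.8%.

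| s | ICC 0.05: SE model / true | Type I | ICC 0.01: SE model / true | Type I |
|---|---|---|---|---|
| 0 | 0.440 / 0.440 | 5.0% | 0.449 / 0.449 | 5.0% |
| 5% | 0.441 / 0.505 | 8.7% | 0.449 / 0.462 | 5.7% |
| 10% | 0.442 / 0.562 | 12.3% | 0.449 / 0.475 | 6.4% |
| 20% | 0.444 / 0.662 | 18.8% | 0.450 / 0.500 | 7.8% |
| 50% | 0.450 / 0.897 | 32.5% | 0.451 / 0.569 | 12.0% |

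Simulation (1,500 runs per setting) agrees within about 2 points. A t-test on site mean changes with 19 df holds about 4% to 6%. With half the SIS baselines missing, the s = 20%, ICC 0.05 case has SEs of 0.566 and 0.747, hence 13.7%. The SD cancels from all these error rates.

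**The case against.** The best defence has five parts.

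- **The two named primary outcomes survive the fallback.** A reader might infer that fixed site removes every treatment comparison. It does not: the mRS and SIS primary contrast is a change and stays estimable. This stands, and the non-estimability point is limited to level contrasts and hazard ratios.
- **Too-small standard errors are not established.** A reader might take the inflation as certain. It needs sites to differ in change over time, and no document gives that variance. The protocol's ICCs belong to a comparison of 12-month levels. With none, type I error is 5%. This stands too. The protocol does, however, link larger ICCs to heterogeneity of the intervention effect, so such variation is foreseen.
- **The fallback may never be used.** It is tempting to argue that at an ICC near 0.01 the fit will often fail. Nothing in the documents shows that, and a site variance estimated at zero is not non-convergence. Nor can a low ICC be used to make the trigger likely while a high ICC supplies the inflation. How often the rule would fire is unknown, but a prespecified rule must be valid when it does.
- **A site-by-time term is not excluded.** SAP 3.1 describes its approach as general, and 3.2 and 3.3 are silent. That is fair, but no such term is named, and a plan should not leave it to be guessed.
- **Extra variance components can themselves cause non-convergence,** especially for binary mRS. True, so a site-level alternative is needed.

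One more inference fails. Protocol 9.B says "this analysis will be implemented using packages such as the SURVIVAL procedure from the SUDAAN package", with the aim of reflecting the hierarchy. It does not say that a marginal Cox model with robust variance was planned.

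**Conclusion.** The fixed-site fallback is wrong as written for the 12-month contrast of the six intermediate factors, the by-visit mRS and SIS differences and the hazard ratios in 4.1. It is equally wrong for 4.3 to 4.5 if they inherit it. That conclusion is algebra and rests on no assumed figure.

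For the mRS and SIS change contrasts the point is conditional. Under fixed site, or under a random site intercept alone, no between-site variance in change enters the standard error. Cancellation is exact on the model scale, identity for SIS and logit for mRS; it is not exact for a change expressed in proportions. The inflation runs from none to 32.5% type I error at ICC 0.05, and to 12.0% at ICC 0.01, over a site-by-time share of 0 to 50%. Missing SIS baselines soften it (18.8% falls to 13.7%). A within-patient correlation of 0.7 worsens it (18.8% becomes 25.9%). These figures are for a continuous outcome and show only the direction for mRS.

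**What to change.** 1. **Delete the fixed-site fallback in SAP 3.1 and 4.1.** State whether 4.3 to 4.5 follow the replacement rule.
2. **On non-convergence,** first try another optimiser or a simpler random structure, and accept a zero site variance estimate as a valid fit. If that fails, use a site-level analysis with df = sites − 2 (19 for 21 sites), or a site-clustered robust variance with a small-sample correction.
3. **For time-to-event outcomes,** fall back to a proportional hazards model with site-clustered variance.
4. **For the mRS and SIS change contrasts,** write out the random effects, add a random site-by-time effect and use site-based df. If that model does not fit, test the change at site level.

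The cost is SAP wording and a few lines of code. Some intervals will be wider.
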